### 7.2 Study Conduct

Summaries of study conduct will be based on all randomized subjects.

#### 7.2.1 Accrual

- Accrual by country and site
- Accrual by region
- Accrual by month randomized

#### 7.2.2 Protocol Deviations

Each subject's data will be examined for deviation from protocol criteria (including violation of eligibility criteria and on-study deviations). ‘Significant’ deviations include those that could have an impact on the primary results of the study, those of ethical concern and those which pose a safety risk to the subject. The ‘Relevant’ deviations are those ‘Significant’ deviations that significantly affect *interpretability of the study results*. (Subjects who never received their

randomized treatment [at least one dose] will also be considered relevant deviations.) Subjects with relevant deviations will be determined programmatically (based on eCRF or central lab data). *Only programmable relevant deviations will be summarized and listed by the statistical team.* Programmable relevant deviation criteria are given in Table 7.2.2-1.

**Table 7.2.2-1: Relevant Protocol Deviation Criteria**

	Timeframe	Deviation Type	Protocol Deviation Specification
E1	Pretreatment	Eligibility	Subjects with wrong diagnosis: Disease Stage at study entry is not Stage IV malignant melanoma
E2	Pretreatment	Eligibility	Subjects with ECOG PS not equal to 0 or 1 during screening period.
E3	Pretreatment	Eligibility	Subject has no lesion (measurable or non-measurable) at screening
P1	On treatment	Not Discontinued	On-treatment laboratory test results that do not meet protocol-specified re-treatment criteria: ALT, AST, TBILI
P2	On treatment	Not Discontinued	Treated subjects whose study drug dosing continued after experiencing drug-related AEs requiring permanent discontinuation per protocol.
P3	On treatment	Incorrect Dosing	Dosing not delayed for Gr 3 or higher skin AE regardless of causality
P4	On treatment	Incorrect Dosing	Dosing not started within 3 days of randomization
P5	On treatment	Incorrect Dosing	Treatment assignment as randomized different from actual treatment given (as per Section 6.2 )
P6	[REDACTED]	[REDACTED]	[REDACTED]

Relevant deviations will be summarized and will be listed by subject.

## **7.3 Study Population**

Summaries of study population will be based on all randomized subjects except: subject disposition (based on all enrolled subjects), time from advanced disease diagnosis to first dose of study therapy (based on all treated subjects).

### **7.3.1 Subject Disposition**

- Disposition of enrolled subjects (number of subjects randomized, treated, not treated [with reason])

### **7.3.2 Demography and Subject Characteristics**

- Age (< 65,  $\geq$  65; summary statistics)
  - The age of a subject is the truncated difference in years between the date of the informed consent and the date of birth, plus 1 day.
- Height (summary statistics)
- Weight (summary statistics)
- Gender (male, female)
- ECOG performance status (0, 1)
- M-substage at study entry (M1a, M1b, M1c)
- Baseline LDH ( $\leq$  ULN,  $>$  ULN)
- Baseline LDH ( $\leq 2 \times$  ULN,  $> 2 \times$  ULN)
- BRAF mutation status (positive, negative, unknown)

The following summaries of factors used in IVRS to stratify subjects will be produced.

- M-substage stratification factor (M1a/M1b, M1c) x BRAF mutation status (yes, no)
- M-substage: stratification factor compared to CRF (M1a/M1b, M1c)
- BRAF mutation status: stratification factor compared to CRF (yes, no)

### **7.3.3 Medical History**

- General medical history (head, eyes, ears, nose, throat; cardiovascular; peripheral vascular; respiratory; gastrointestinal; hepatobiliary; renal; genitourinary; endocrine-metabolic; hematologic-lymphatic; musculoskeletal; dermatologic; neurologic; psychiatric; immunology/allergies; neoplasia; alcohol use; tobacco use; drug abuse)

### **7.3.4 Disease Characteristics**

- Time from advanced disease diagnosis to first dose of study therapy (summary statistics)
- Baseline TA (site of disease, number of disease sites)
- Baseline target lesions (number and site of target lesions, procedures for evaluating target lesions; summary statistics and quartiles of sum of reference diameters of target lesions)
  - TAs on or prior to first dose date will be considered as baseline. The latest assessment for each lesion will be considered.
- Melanoma subtype (mucosal, cutaneous, acral, ocular/uveal, and other)

### **7.3.5      *Prior Therapy***

- Prior therapy (systemic cancer, radiotherapy, surgery related to cancer)
- Duration of prior systemic therapy (summary statistics)

### **7.3.6      *Clinical Complaints and Findings***

Events with onset prior to the date of first dose will be examined (whether recorded on the pre-treatment events CRF or on the on-treatment adverse events CRF).

- Pre-treatment events (worst CTC grade of any event and of events by SOC)

### **7.3.7      *Baseline Laboratory Examinations***

- Baseline hematology (CTC grade for hemoglobin, WBC, ANC, platelet count, ALC)
- Baseline liver function (CTC grade for ALT, AST, total bilirubin, ALP)
- Baseline renal function (CTC grade for creatinine)
- Baseline pancreatic function: (CTC grade for amylase)

## **7.4            *Extent of Exposure***

Summaries of exposure will be based on all treated subjects, except for the summary for subsequent therapies (based on all randomized subjects).

### **7.4.1      *Administration of Study Therapy***

- Time from randomization to first dose of ipilimumab (0 to 3 days, > 3 to 7, > 7 to 14, > 14 to 21, > 21 to 28, > 28)
- Number of doses of study therapy (summary statistics)
- Cumulative dose of study therapy (summary statistics)

Cumulative dose of ipilimumab/dacarbazine in mg is defined as the sum of all calculated doses (mg) at each dosing. Cumulative dose of ipilimumab in mg/kg and dacarbazine in mg/m^2 is defined as the sum of all doses (in mg/kg and mg/m^2 respectively) received by the subject.

Ipilimumab dose in mg/kg is calculated as the dose in mg divided by the most recent weight in kg prior to infusion. If the subject's weight is missing, the last observation carried forward approach will be used.

Dacarbazine dose in mg/m^2 is calculated as the dose in mg divided by the most recent body surface area (BSA) prior to infusion. BSA is derived from most recent weight and baseline height. If the subject's weight is missing, the last observation carried forward approach will be used.

Cumulative dose will be listed by subject.

### **7.4.2      *Discontinuation from Induction Phase***

Failure to complete the (re-)induction phase will be tabulated.

- Number of subjects who completed or failed to complete (with reason) the (re-)induction phase.

- Discontinuation from study therapy in induction phase (subjects with study therapy discontinued, reason for discontinuation).
- Discontinuation from ipilimumab in re-induction phase (subjects with study therapy discontinued, reason for discontinuation).

#### **7.4.3      *Interruption of Infusion or Delay of Study Therapy***

An infusion interruption refers to an interruption of the infusion of study therapy, whether or not the infusion is resumed. A dose delay refers to a delay in the administration of ipilimumab (but not a discontinuation thereof) relative to the protocol schedule. A dose omission refers to an omission in the administration of DTIC (but not a discontinuation thereof) relative to the protocol schedule.

- Infusion interruption in induction phase (subjects with at least one interrupted dose, reason for first dose interruption, number of interruptions).
- Infusion rate reduction in induction phase (subjects with at least one infusion with IV rate reduced, reason for first infusion IV rate reduced, number of infusions with IV rate reduced).
- Dose delay of ipilimumab in induction phase (subjects with at least one delayed dose, reason for first dose delay, number of delays).
- Dose omission of DTIC in induction phase (subjects with at least one omitted dose, reason for first dose omitted, number of omissions).
- Infusion interruption of ipilimumab in re-induction phase (subjects with at least one interrupted dose, reason for first dose interruption, number of interruptions).
- Infusion rate reduction of ipilimumab in re-induction phase (subjects with at least one infusion with IV rate reduced, reason for first infusion IV rate reduced, number of infusions with IV rate reduced).
- Dose delay of ipilimumab in re-induction phase (subjects with at least one delayed dose, reason for first dose delay, number of delays).

#### **7.4.5      *Other On-Study Therapy***

Non-protocol-specified medical treatment procedures which occur on-study (i.e. on or after the first day of study therapy and within 90 days following the last dose of study therapy) will be summarized and listed.

- On-study surgery (with reason)
- On-study radiotherapy (with reason)

## **7.4.6 Subsequent Therapy**

Therapies received subsequent to discontinuation of study therapy will be summarized and listed.

- Frequency of subsequent systemic therapies by medication class and generic name
- Frequency of subsequent systemic therapy type (any, and classes, e.g.: immunotherapy only, chemotherapy only, immunotherapy and chemotherapy, other)
- Frequency of subsequent surgery
- Frequency of subsequent radiotherapy
- Time from randomization to first subsequent therapy (median, range)
- Listing of subsequent therapies (including dates of therapy)

## **7.5 Efficacy**

All hypothesis testing will be two-sided and will be based upon a significance level of 0.20.

No type I error rate multiplicity adjustment will be made for secondary endpoint testing. P-values associated with the comparisons of OS, DCR and PFS will be purely descriptive in nature. All efficacy analyses will be based on all randomized subjects, as randomized, unless indicated.

### **7.5.1 Survival Rates at Specified Time Points**

Yearly survival rates will be calculated for each treatment group using the KM product-limit method, along with their corresponding log-log transformed 80% CIs.

Two-year survival rate is the primary endpoint. The survival rate at 2 years will be compared between treatment group using a chi-square test stratified by M substage (M1a+M1b versus M1c) and BRAF mutation status (yes vs no), as recorded in the IVRS. The stratified chi-square test is defined by the following formula:

$$\chi^2 = \frac{\left( \sum_{s=1}^m \hat{S}_{1s}(t) - \hat{S}_{2s}(t) \right)^2}{\sum_{s=1}^m \hat{V}(\hat{S}_{1s}(t)) + \hat{V}(\hat{S}_{2s}(t))},$$

where  $\hat{S}_{ks}(t)$  and  $\hat{V}(\hat{S}_{ks}(t))$  be the Kaplan-Meier estimate and variance based on the Greenwood formula for the  $s$ th stratum in the  $k$ th treatment group at time  $t$ .

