#### **4.2.2 Overall Survival**

OS is defined for each subject as the time between randomization date and the date of death (of any cause). If a subject has not died, the subject will be censored at the time of last contact (last known alive date).

A modified variable will be examined for the purposes of sensitivity analysis:

- OS accounting for subsequent PD-1/PD-L1 therapy will be defined through addition of the following restriction to the primary definition: subjects who receive subsequent PD-1/PD-L1 cancer therapy will be censored at the start date of subsequent PD-1/PD-L1 therapy.

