## 5 SAMPLE SIZE AND POWER

Approximately 180 Chinese subjects will be randomized to ipilimumab and DTIC at a 2:1 ratio and followed at least 2 years after randomization to ensure 80% power through simulation using a chi-squared test with a Type I error rate of 0.20 to reject the null hypothesis of no difference in 2-year survival rate between treatment groups, assuming a HR [ipilimumab vs DTIC] of 0.67. Under an exponential distribution, this hazard ratio (HR) would correspond to an 12 month median OS for the ipilimumab arm with an 8 month median OS in the DTIC arm^8(or equivalently 25% and 12.5% in the ipilimumab and DTIC arm). The accrual duration is approximately 18 months, assuming a monthly rate of 10 subjects per month. The primary analysis will be performed about 42 months after the first subject is randomized.

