#### **7.5.1.1 Subgroup Analyses**

Two-year survival rates along with two-sided 80% CI based on the log-log transformation will be presented within subsets defined by information recorded on the baseline CRF.

This summary and comparison based on the unstratified chi-square test will be provided for the following subgroups:

- by age (< 65,  $\geq$  65)
- by gender (male, female)
- by M-Substage at study entry (M1a/M1b, M1c)
- by ECOG performance status (0, 1)

- by baseline LDH ( $\leq$ ULN,  $>$  ULN)
- by baseline LDH ( $\leq 2 \times$  ULN,  $> 2 \times$ ULN)
- by BRAF mutation status (positive, negative, unknown)
- by subtype (acral, cutaneous, other)

In case a subgroup includes less than 10 subjects, the analysis for the given subgroup will not be carried out (or the possibility of combining subgroups will be considered).

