### **7.5.1.2 Sensitivity Analyses**

The following analyses will be conducted

- An unstratified chi-square test will be performed to compare survival rate at 2 years after randomization between treatment groups
- The stratified and unstratified chi-square tests based on the modified OS accounting for subsequent PD-1/PD-L1 therapy.

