#### **7.5.4 Disease Control Rate**

Exact, two-sided 80% CI for DCR within treatment group will be calculated using the method of Clopper and Pearson.

For the comparison of DCR between treatment groups, a Cochran-Mantel-Haenszel (CMH) test with an associated odds ratio estimate and exact two-sided 80% CI, stratified by M substage (M1a+M1b versus M1c) and BRAF mutation status (yes vs. no), as recorded in the IVRS, will be applied.

- Summary of DCR (primary definition)
- Comparison of DCR (primary definition)
- Summary of DCR (per protocol definition)
- Comparison of DCR (per protocol definition)

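### The primary 2-year survival test in SAP 7.5.1 gives its four strata equal weight and has no stated rule for a stratum-arm without a 2-year survivor, and SAP 5 gives no stratum assumptions for its 80% power

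*SAP*

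**What the plan says.** - **SAP 7.5.1** compares 2-year survival with a chi-square stratified by M-substage (two levels) and BRAF status (two levels) from the IVRS, which makes four strata. It introduces the statistic with "The stratified chi-square test is defined by the following formula". The statistic is the squared plain sum of the stratum differences over the plain sum of their variances. The only terms defined are the "Kaplan-Meier estimate and variance based on the Greenwood formula" for each stratum and arm. No weight appears.
- **SAP 5** plans about 180 subjects, 2:1, "to ensure 80% power through simulation using a chi-squared test with a Type I error rate of 0.20", with 25% vs 12.5% alive at 2 years. It gives one rate per arm and no stratum sizes, rates or weights.
- **SAP 7.5.1.1** has the only small-number rule: "In case a subgroup includes less than 10 subjects, the analysis for the given subgroup will not be carried out". It concerns subgroup analyses and counts subjects, not survivors.
- **SAP 7.5.1.2** adds two checks: "An unstratified chi-square test will be performed to compare survival rate at 2 years after randomization between treatment groups", and "The stratified and unstratified chi-square tests based on the modified OS accounting for subsequent PD-1/PD-L1 therapy".
- **SAP 7.5.4** compares disease control rate on the same two factors with "a Cochran-Mantel-Haenszel (CMH) test with an associated odds ratio estimate".
- **SAP 8** leaves room for further conventions in the Data Presentation Plan, which is not among the documents.

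**The concern.** There are two separate problems in the test of the primary endpoint.

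**Weights.** With equal weights the noisiest stratum contributes as much to the numerator as the largest and dominates the variance. The test then addresses an equal-weight average over strata, not the 2-year difference in the randomised population. If the strata are uneven and the effect is similar in each, power is lost. A CMH test does not do this, because it weights by stratum size.

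**Empty cells.** If everyone in a stratum-arm has died by 24 months, the Kaplan-Meier estimate is 0 and Greenwood's expression becomes zero times a division by zero. Software or programmer may set the variance to 0, drop the stratum, or return no result. Two people following the SAP could report different primary p-values.

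**Working it through.** **Inputs.** 120 vs 60 subjects, 25% vs 12.5%, two-sided 0.20 (SAP 5 and 7.5). All subjects have at least 2 years of follow-up (SAP 7.1), so without loss to follow-up the Kaplan-Meier rate is a simple proportion. Stratum shares are my assumption, with the two factors taken as independent and the same rates in every stratum.

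**1. The plan's own figure.** Unstratified, unpooled:

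variance = 0.25×0.75/120 + 0.125×0.875/60 = 0.001563 + 0.001823 = 0.003385; SE = 0.0582; z = 0.125/0.0582 = 2.148; power ≈ Φ(2.148 − 1.282) = 0.807.

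Exact binomial enumeration gives power 0.800 and type I error 0.209 (12.5% in both arms). The 80% reproduces.

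**2. Effect of equal weights.** With stratum shares p_s, the printed sum has efficiency 16/Σ(1/p_s) relative to size weighting. For 30% BRAF-positive and 60% M1c the shares are 0.18, 0.42, 0.12 and 0.28:

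Σ(1/p_s) = 5.56 + 2.38 + 8.33 + 3.57 = 19.84; efficiency = 0.806; z = 2.148×√0.806 = 1.929; power ≈ Φ(0.647) = 0.74.

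**3. Simulation of the printed test** (400,000 trials per case; type I error at 12.5% in both arms):

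| BRAF+/M1c (%) | Power, empty cell variance 0 | Type I error | Power, empty stratum dropped | Type I error |
|---|---|---|---|---|
| 50/50 | 0.804 | 0.219 | 0.659 | 0.165 |
| 40/60 | 0.784 | 0.222 | 0.618 | 0.155 |
| 30/60 | 0.748 | 0.231 | 0.554 | 0.145 |
| 20/60 | 0.686 | 0.252 | 0.450 | 0.136 |
| 15/60 | 0.640 | 0.278 | 0.409 | 0.139 |

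**4. How often a DTIC cell is empty.** Four equal strata have 15 DTIC subjects each: 0.875^15 = 0.135, and 1 − (1 − 0.135)^4 = 0.44. At 30/60 the DTIC cells are 11, 25, 7 and 17: 1 − (0.770×0.965×0.607×0.897) = 0.60.

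**5. Effect differing by BRAF status,** 30/60 mix, overall still about 25% vs 12.5%. Power of the printed test is 0.82 if ipilimumab survival is 32% in BRAF-positive and 22% in BRAF-negative subjects, and 0.67 if it is 18% and 28%.

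**6. Larger trial.** Protocol 3.1 reports 258 enrolled. SAP 6.3 counts as enrolled anyone consented and registered, so 258 is an upper bound on the number randomised. At 258, printed power for the five mixes (variance 0) is 0.90, 0.88, 0.84, 0.77 and 0.71, against 0.893 unstratified. An empty DTIC cell occurs in 20% to 69% of trials.

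**7. Alternatives at N = 180, over the five mixes.**

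| Size-weighted test | Power | Type I error |
|---|---|---|
| Unpooled variances, no empty-cell rule | 0.804–0.805 | 0.218–0.219 |
| Unpooled variances, null variance in empty-cell strata only | 0.798–0.799 | 0.205–0.212 |
| Null variance in all strata | 0.775–0.776 | 0.200–0.201 |

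The 0.205–0.212 covers nulls of 12.5% and 20.8% in both arms; the other two rows are at 12.5%.

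**The case against.** **The formula is explicit and pre-specified.** It sums over all strata, so dropping one departs from it. Without censoring, Greenwood reduces to S(1−S)/n, which is 0 at S = 0. On that reading equal strata give 0.804 and 0.219, close to the unstratified test. This stands as the most natural reading, but the SAP does not state it and software need not follow it.

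**The weighting loss rests on assumed shares.** This also stands. At 50/50 and 40/60 the loss is 0 to 2 points, and a larger effect in BRAF-positive subjects would raise power.

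**The unstratified test and the stratum table (SAP 7.3.2) are already planned,** and arm-level survival rates and intervals are untouched. So a divergence would be visible. But a sensitivity analysis does not define the primary p-value, and the stratified PD-1/PD-L1 check has the same gap.

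A reader might infer three stronger things that the documents do not support:
- *That the 80% was computed for an unstratified test.* SAP 5 does not describe its simulation. The printed test with four equal strata also gives about 0.80.
- *That the printed test inflates type I error.* This holds if empty cells get variance 0. If the stratum is dropped, the error falls below 0.20. The unstratified unpooled test is itself at 0.209, so not all of the excess comes from stratification.
- *That the programmers had no rule.* The SAP has none, but the Data Presentation Plan may.

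**Conclusion.** The point holds in limited form. Two facts come straight from the text: the primary statistic carries no stratum weights, and the SAP has no rule for a stratum-arm without a 2-year survivor. The second does not depend on the stratum mix; with equal strata it arises in 44% of trials at the planned rates, and the choice of convention then moves power between 0.80 and 0.66.

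The cost of equal weighting is conditional. It is 0 to 16 points of power over the mixes tried (0.80 to 0.64), assuming a similar effect in every stratum, no loss to follow-up and variance 0 in empty cells. It may be small in the actual trial. SAP 5's 80% fits an unstratified test or equal strata, but not the printed test with uneven strata and a similar effect. It should be fixed, but it does not invalidate the trial.

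**What to change.** 1. **Weight the strata.** Use w_s = n1s·n2s/(n1s + n2s) and chi-square = [Σ w_s(S1s − S2s)]² / Σ w_s²·V_s, keeping the SAP's unpooled Greenwood variances for V_s.
2. **Add one sentence for empty cells.** Where an arm has no survivor at 24 months, use for that stratum only the null variance: V_s = [N_s²/(n1s·n2s)]·[N_s/(N_s − 1)] times the Greenwood variance of the both-arms Kaplan-Meier estimate. A stratum with no survivor in either arm adds nothing.
3. **Restate SAP 5** with the stratum assumptions and the power of this test.
4. **Apply the same weights and rule to the stratified PD-1/PD-L1 check,** without claiming a type I error of 0.20. Under SAP 4.2.2, "subjects who receive subsequent PD-1/PD-L1 cancer therapy will be censored at the start date of subsequent PD-1/PD-L1 therapy", so censoring may differ by arm. With assumed yearly loss of 5% vs 30% or 10% vs 40% (ipilimumab vs DTIC), type I error is 0.221–0.244 for this test and 0.256–0.334 for the printed one.
5. **Report after the fact.** Protocol 5.4.1 gives database lock as 03Jun2019. Put the weighted test in a dated addendum labelled post hoc, beside the pre-specified stratified result and the unstratified test. Give the stratum-by-arm counts and the empty-cell convention actually used. Do not replace the pre-specified result.

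The cost is one formula, one sentence, one power re-run and the addendum, with no new data or patients. Power stays at about 0.80, and type I error at about 0.205–0.21 under similar censoring. Using the null variance in all strata is a trade-off, not the main fix: type I error is 0.20, but power falls to about 0.775, and about 195 subjects would be needed to regain 0.80.

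### The primary 2-year survival test uses arm-specific Greenwood variances, so at the design inputs it rejects in ipilimumab's favour about 12–12.5% of the time under the null (nominal 10%) and 21–22% overall (stated 20%)

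*SAP*

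**What the plan says.** SAP 7.5.1 compares 2-year survival with a stratified chi-square over four strata (M substage by BRAF status). The numerator is the square of the plain sum over strata of the differences between arms in Kaplan-Meier estimates. The denominator is the sum of the variances, with each term the "Kaplan-Meier estimate and variance based on the Greenwood formula for the" stratum and arm concerned. Everything is on the raw survival scale. The confidence intervals in the same section use the log-log scale.

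On the level, SAP 7.5 says "All hypothesis testing will be two-sided and will be based upon a significance level of 0.20". SAP 5 plans "to ensure 80% power through simulation using a chi-squared test" at the same 0.20 level, "assuming a HR [ipilimumab vs DTIC] of 0.67", with 2-year rates of "25% and 12.5% in the ipilimumab and DTIC arm".

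SAP 7.5.1.2 adds a sensitivity analysis: "An unstratified chi-square test will be performed to compare survival rate at 2 years after randomization between treatment groups". Neither that section nor the subgroup section (7.5.1.1) gives a variance formula for the unstratified test.

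**The concern.** A variance estimated separately in each arm moves with that arm's estimate. When survival is well below 50%, a low estimate has a small variance. DTIC is the smaller arm and supplies most of the variance of the difference. When DTIC survival is low by chance, the difference favours ipilimumab and the denominator shrinks. When DTIC survival is high by chance, the denominator grows. The test therefore rejects too often in one direction.

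That direction is the superiority hypothesis in Protocol 1.2. This is also the trial's only confirmatory test, because SAP 7.5 makes the OS, PFS and DCR p-values descriptive. The level is already a lenient 0.20, so the actual error rate should be known and should match the stated one.

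**Working it through.** **Inputs.** From SAP 5: about 180 subjects at 2:1 (120 and 60), rates of 25% and 12.5%, and at least 2 years of follow-up. From SAP 7.5: two-sided 0.20, so 10% in each direction and a critical value of 1.2816² = 1.642. With no censoring before 24 months, the Kaplan-Meier estimate is a proportion p and Greenwood's variance is p(1−p)/n.

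**The plan's own figures.** Exponential medians of 12 and 8 months give 2^(−24/12) = 25% and 2^(−24/8) = 12.5%. For power:

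- Unpooled: SE = √(0.25×0.75/120 + 0.125×0.875/60) = 0.0582. Power = Φ(0.125/0.0582 − 1.2816) = 80.7%. Exact binomial enumeration gives 80.0%.
- Pooled: the mean rate is (30 + 7.5)/180 = 0.2083 and SE₀ = √(0.2083×0.7917×(1/120 + 1/60)) = 0.0642. Power = Φ((0.125 − 1.2816×0.0642)/0.0582) = 76.9%. Exact enumeration gives 77.4%.

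The stated 80% is reproduced, but of the two-sided 0.20 forms only by the unpooled one.

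**How the tilt arises.** Take ipilimumab at 15/120 (12.5%).

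- DTIC 4/60: difference 0.0583, Greenwood variance 0.000911 + 0.001037 = 0.001948, chi-square 1.75. This rejects.
- DTIC 11/60: same distance in the other direction, variance 0.000911 + 0.002495 = 0.003407, chi-square 1.00. This does not reject.
- DTIC 4/60 with a pooled variance: 0.1056×0.8944×0.025 = 0.002360, chi-square 1.44. This does not reject.

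**Null error, unstratified form, exact.** This is a sum over Binomial(120, p) × Binomial(60, p) and needs no stratum assumption.

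| Common rate | Variance | Toward ipilimumab | Toward DTIC | Total |
|---|---|---|---|---|
| 12.5% | separate arms | 12.2% | 8.7% | 20.9% |
| 20% | separate arms | 11.4% | 9.2% | 20.6% |
| 25% | separate arms | 11.1% | 9.6% | 20.6% |
| 12.5% | pooled | 9.8% | 10.5% | 20.3% |

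**Null error, stratified formula, simulated.** At least 200,000 trials per setting, common rate 12.5%. Stratum shares are assumptions.

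| Test | Strata | Toward ipilimumab | Total |
|---|---|---|---|
| As written | four equal | 12.4–12.6% | 21.9% |
| As written | M1c 50%, BRAF-positive 40% | about 12.8% | about 22% |
| As written | M1c 50–60%, BRAF-positive 20–25% | about 13.6–16.0% | about 23–26% |
| Equal weights, pooled variance | all mixes | 10.1–10.6% | 20.7–22.2% |
| Mantel-Haenszel weights, Greenwood kept | all mixes | about 12.5% | about 21.9% |
| Mantel-Haenszel weights, pooled variance | all mixes | about 10% | 20.6–20.9% |

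At a 25% rate the formula as written gives about 11.5% and 21.5% with equal strata, and 12.4–14.0% and 22.8–24.8% with the uneven mixes. With full Kaplan-Meier estimation, uneven strata and 5–10% assumed dropout (12,000 trials per setting), it gives 14.7–15.5% and 24.4–25.8% at a 12.5% rate.

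Changing only the variance removes nearly all of the tilt. Changing only the weights leaves it at about 12.5%. The variance creates the tilt, and the unweighted sum over small strata amplifies it. Moving to the log-log scale with equal weights does not repair the stratified test (11.4–15.6% and 21.6–27.0%).

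**Power at 25% against 12.5%.** The formula as written gives about 80% with equal or nearly equal strata and about 68–74% with the uneven mixes. Mantel-Haenszel weights with a pooled variance give about 78% throughout.

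**The case against.** The strongest reply is that this is ordinary large-sample error in a Wald-type test. The trial is Phase II with a deliberately lenient level, and the formula is fully prespecified, so it leaves the analyst no discretion. An excess of 1 to 2 points in total is small, and it shrinks as survival rises. All of that stands, and it limits how serious the point is. It does not remove the lean toward the trial's own hypothesis.

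Three stronger readings are tempting, and the documents do not support them.

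- A reader might take 13–16% as the error rate of the plan. It needs small uneven strata, and neither document gives expected M-substage or BRAF shares. It also needs the unweighted sum, so it is not the effect of the variance alone.
- A reader might say that the unstratified sensitivity test has the same tilt. SAP 7.5.1.1 and 7.5.1.2 give no variance for it, and a pooled chi-square would not be tilted (9.8% toward ipilimumab). The 80% power suggests that the unpooled form was in mind, but that is an inference.
- A reader might conclude that the 80% power is wrong. It reproduces exactly with the unpooled form. About 2.6 points of it (80.0% less 77.4%) go with the more liberal variance.

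The sample could also be larger than planned. Protocol 3.1 reports 258 enrolled but not the number randomized. If all 258 were randomized 2:1, the formula as written would give 11.9–14.6% toward ipilimumab and 21.3–24.1% in total at a 12.5% rate.

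**Conclusion.** The point holds at a modest size. At N = 180, 2:1, a common rate of 12.5% and no censoring, the primary test has an error of about 12–12.5% toward ipilimumab and 21–22% in total. At a 25% rate these fall to about 11–11.5% and 20.6–21.5%. With small uneven strata, which are assumed, they may reach about 13–16% and 22–26%. In every setting examined the total exceeds 0.20 and the larger share lies on the ipilimumab side.

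The stratified figures assume equal survival across strata. One run with prognostic strata gave 14.5% and 24.6%, within the uneven range. This should be fixed, but it does not by itself invalidate the primary comparison.

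**What to change.** In SAP 7.5.1, compute the variance under the null by pooling the two arms within each stratum, and combine strata with Mantel-Haenszel weights. When every subject's status at 24 months is known, this is in effect the CMH test that SAP 7.5.4 already uses for DCR. With earlier censoring the two are not equivalent. In that case, use a Greenwood variance built from the pooled Kaplan-Meier estimate and each arm's own numbers at risk, and check the error by simulation, since the figures here for the pooled variance assume no censoring.

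State in SAP 7.5.1.2 that the unstratified test uses the null variance too, and restate the power in SAP 5 as about 78%.

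The cost is one formula, one programming step and a sentence on power. A small excess remains (20.6–20.9% in total), without the lean toward ipilimumab. Actual power falls by about 2 points if strata are nearly equal and rises to about 78% if they are clearly uneven.

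Protocol 1.2 gives a database lock of 03Jun2019. If the analysis has been run, keep the prespecified result as primary and report the null-variance result beside it, labelled post hoc, with the actual error rate of the prespecified test at the observed stratum sizes.
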